4 STUDY DESIGN

4.1 Study Overview

This is a Phase I/II open-label dose-finding trial among lung transplant recipients who received three or four mRNA vaccine doses (mRNA-1273 or BNT162b2) after lung transplantation to: standard-dose (50 ug), mid-dose (100 ug) or high-dose (200 ug) mRNA-1273 booster vaccine. Participants will be enrolled into three dose groups: 1) Standard-dose (50 ug) – 20 participants, 2) Mid-dose (100 ug) – 20 participants, 3) High-dose (200 ug) – 20 participants. The first 2 participants in both the mid-dose and high dose groups will be considered the ‘sentinel’ group. Participants in the sentinel group will receive the vaccine and undergo a 7-day observation period for safety and reactogenicity before additional participants are enrolled into that dose group.

Overall study enrollment will begin with the mid-dose sentinel group (n=2). During the observation period for the mid-dose sentinel group, we will enroll two participants into the standard-dose group. Once the mid-dose sentinel group completes their 7-day observation period without triggering halting rules and is approved to proceed by the DSMB, we will enroll the next 27 participants (Cohort 1) with a 2:1 randomization into the mid-dose (n=18) and standard-dose (n=9) groups.

Once all 20 participants have received their mid-dose vaccine without triggering halting rules and is approved to proceed by the DSMB, we will enroll the high-dose sentinel group (n=2). Once the high-dose sentinel group completes their 7-day observation period without triggering halting rules and is approved to proceed by the DSMB, we will enroll the next 27 participants (Cohort 2) with a 2:1 randomization into the high-dose (n=18) and standard-dose (n=9) groups. Thus, all 20 participants in the mid-dose group will be enrolled prior to enrollment of the high-dose group.

We will perform stratified randomization for the two cohorts based on: 1) the number of prior doses, and 2) prior receipt of any BNT162b2 vaccines. Randomization will be done by the UCLA Clinical and Translational Science Institute (CTSI) statistics team based on scheduled participants prior to the study visit. The 6 participants in the sentinel (n=4) and initial (n=2) groups (Table 1) will be assigned into the 3 groups based on their scheduled visit day.

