10.2 Visit 1 Day 1 (Clinic): Booster Vaccine Day

1. For participants who meet inclusion/exclusion criteria, the investigator team will again review the study with the participant (or participant's legal representative) in person and obtain written informed consent and HIPAA authorization.
2. Record demographic data.
3. Record medical history.
4. Review of birth control history with female participants of childbearing potential (<1 year since start of menopause).

5. For women of childbearing potential, counsel participants to use adequate birth control methods required during the trial to avoid pregnancy.
6. For women of childbearing potential, urine pregnancy test will be checked prior to study drug administration on Visit 1 (Day 1).
7. Confirmation participants meet all inclusion criteria and no exclusion criteria review.
8. Review pre-study concomitant medications and therapies and record on the appropriate CRF.
9. Review of influenza and any all 2019-CoV vaccinations or other experimental coronavirus vaccines.
10. Vital signs (HR, BP, temperature, oximetry), and height and weight for determination of BMI.
11. Full physical exam will include assessments of the following organs and organ systems: skin, head, ears, eyes, nose, and throat (HEENT), neck, lungs, heart, liver, spleen, abdomen, extremities, lymph nodes (axillary and cervical), and nervous system.
12. Obtain blood samples for baseline: Total immunoglobulins (IgG, IgA, IgM), anti-RBD, anti-spike binding and neutralizing antibody levels, PBMCs collected for cellular response assays including flow cytometry with intracellular staining, whole blood collected for cellular response assays, troponin / CK and cytokines for storage.
13. Confirm group assignment: standard-dose, mid-dose or high-dose group.
14. Inform participants of their designated dose.
15. Administration of booster vaccine.
16. Participants will be observed for 30-minutes post injection administration.
17. Dispense daily diary of symptoms for first 7 days after injection dispensed to participant measuring FDA Toxicity Grading Scale and adverse events.

10.3 Visit 2 Day 3 +/-1 Day (Phone – 2 days post booster):

1. All participants will complete a daily diary of solicited and unsolicited AEs from the vaccination until 7 days post-vaccination. Reactogenicity will be measured by the occurrence of solicited injection site and systemic reactions for the first 7 days post-vaccination utilizing the FDA Toxicity Grading Scale.

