2. Participants will be contacted by telephone to query for safety events and review daily diaries. Based on the information collected, participants may be asked to return to the clinic for evaluation for an unscheduled visit.
3. Review daily diaries, AEs (solicited and unsolicited), SAEs, AESIs and MAAEs.
4. Participants will contact their primary care doctor, lung transplant pulmonologist or study principal investigator with any SAEs, AESIs or MAAEs.

10.4 Visit 3 Day 7 +/-2 Days (Clinic Visit – 6 days post booster):

1. Vital signs (HR, BP, temperature, oximetry), and height and weight for determination of BMI.
2. Symptom-directed (targeted) physical exam. Targeted physical examinations should also include an assessment for signs suggestive of AEs and AESIs. Interim or unscheduled physical examinations will be performed at the discretion of the PI or appropriate sub-investigator, if necessary, to evaluate AEs or abnormal clinical laboratory test results.
3. Obtain blood samples for follow-up: Total immunoglobulins (IgG, IgA, IgM), anti-RBD, anti-spike binding and neutralizing antibody levels, PBMCs collected for cellular response assays including flow cytometry with intracellular staining, whole blood collected for cellular response assays, troponin / CK and cytokines for storage.

5. Review daily diaries, AEs (solicited and unsolicited), SAEs, AESIs and MAAEs.

10.5 Visit 4 Day 30 +/- 7 Days (Clinic – 29 days post booster):

1. Vital signs (HR, BP, temperature, oximetry), and height and weight for determination of BMI.
2. Symptom-directed (targeted) physical exam. Targeted physical examinations should also include an assessment for signs suggestive of AEs and AESIs. Interim or unscheduled physical examinations will be performed at the discretion of the PI or appropriate sub-investigator, if necessary, to evaluate AEs or abnormal clinical laboratory test results.
3. Obtain blood samples for follow-up: Total immunoglobulins (IgG, IgA, IgM), anti-RBD, anti-spike binding and neutralizing antibody levels, PBMCs collected for cellular response assays including flow cytometry with intracellular staining, whole blood collected for cellular response assays, troponin / CK and cytokines for storage.
4. Review daily diaries, AEs (solicited and unsolicited), SAEs, AESIs and MAAEs.

10.6 Visit 5 Day 90 +/- 7 Days (Phone – 89 days post booster):

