Frequency and grade of each solicited AE (local and systemic reactogenicity) will be collected until Day 7 using the FDA Toxicity Grading Scale to be recorded on a daily diary. Frequency and grade of each unsolicited AEs will be collected until Day 30. Frequency of any SAEs, AESIs and MAAEs will be collected until Day 180. After Day 30 through the end of study on Day 180, only SAEs, AESIs and MAAEs will be reported as AEs. All AEs, solicited and unsolicited, will be captured on the appropriate CRF. Information to be collected for AEs includes event description, date of onset, assessment of severity, relationship to study product and alternate possible etiology, date of resolution, seriousness, and outcome. AEs occurring during the study-collection and reporting period will be documented appropriately regardless of relationship. AEs will be followed to resolution or stabilization.

Solicited Adverse Events:

Solicited AEs are anticipated local and systemic AEs for which consistent collection of information is desired. Study clinicians will follow and collect resolution information for any reactogenicity symptoms that are not resolved within 7 days. Solicited AEs (i.e., reactogenicity) will be collected using a daily diary and recorded on the appropriate CRF from the time of the vaccination until 7 days post vaccination (Days 1-7). For this study, solicited AEs will be defined and graded as follows (Tables 3):

Table 3: Solicited Adverse Reactions and Grading

Phase I/II, Open-label Dose-finding Trial of High-Dose mRNA-1273 Booster for Lung Transplant Recipients
Confidential

Reaction	Grade 0	Grade 1	Grade 2	Grade 3	Grade 4
Injection site pain	None	Does not interfere with activity	Repeated use of over-the-counter pain reliever > (greater than) 24 hours or interferes with activity	Any use of prescription pain reliever or prevents daily activity	Requires emergency room visit or hospitalization
Injection site erythema (redness)	< (less than) 25 mm or < 2.5 cm	25 - 50 mm or 2.5 - 5 cm	51 - 100 mm or 5.1 - 10 cm	> 100 mm or > 10 cm	Necrosis or exfoliative dermatitis (severe skin rash causing skin discoloration or peeling)
Injection site swelling/induration (hardness)	< 25 mm or < 2.5 cm	25 - 50 mm or 2.5 - 5 cm	51 - 100 mm or 5.1 - 10 cm	> 100 mm or > 10 cm	Necrosis (severe swelling with skin discoloration, blistering, or peeling)

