11.2 Serious Adverse Experiences (SAE)

An SAE is defined as any AE occurring at any dose that results in any of the following outcomes:

1. death
2. a life-threatening adverse experience
3. inpatient hospitalization or prolongation of existing hospitalization
4. a persistent or significant disability/incapacity
5. a congenital anomaly/birth defect

Other important medical events may also be considered an SAE when, based on appropriate medical judgment, they jeopardize the participant or require intervention to prevent one of the outcomes listed.

Participants will be instructed to call a study team line (attended 24-hours per day) if they experience any grade 4 symptom from the "Solicited Adverse Reactions and Grading" table (Table 3), any severe unsolicited AE (Table 4), or any SAE. The study team member will interview, document and triage the participant for further evaluation.

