12.3 Halting Criteria for Full Group (Cohorts 1 and 2)

The study will be paused if any of the following events occur in the full group (standard (n=18), mid (n=18) and high dose (n=18) groups) and enrollment may resume only after the DSMB reviews the events and permits the study to continue.

1. Any grade 4 (Table 3) solicited local or systemic reaction in the mid or high-dose groups considered to be at least possibly related to vaccination within 7 days after administration of the vaccine.
2. Three or more grade 3 (Table 3) solicited local or systemic reaction in the same dose group considered to be at least possibly related to vaccination that lasted at least 48 hours within 7 days after administration of the vaccine.
3. Any three participants with severe allergic reaction that is at least possibly related to vaccination within 24 hours after administration of the vaccine.
4. Any SAE within 28 days after administration of the vaccine considered to be at least possibly related to vaccination.
5. Any episode of myocarditis / pericarditis within 28 days after administration of the vaccine.
6. Any new episodes of elevated troponin, ECG and physical exam findings concerning for myocarditis / pericarditis within 28 days after administration of the vaccine.
7. Any death unless determined to be definitely not related to vaccination within 90 days after administration of the vaccine.

If the halting criteria is triggered for the high-dose group and further enrollment of this group is not recommended by the study investigators, DSMB or IRB, the study will continue randomized enrollment into the mid-dose and standard-dose groups with a 1:2 ratio to complete the enrollment of 60 participants total. Since the expected immunogenicity difference between these two groups will be smaller, we will require more participants to detect a difference between these two groups. The 1:2 enrollment ratio into the mid-dose and standard-dose groups will even the distribution of participants into these two groups. The primary endpoint analysis for safety and reactogenicity will not be affected by a restriction of participants into the mid-dose and standard-dose groups.

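### Small safety gain at low cost: require 7 completed days on all 20 mid-dose recipients before the 200 ug sentinels open, as the two sentinel gates already do

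*Combined protocol and SAP*

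**What the plan says.** The plan has three gates that combine a safety condition with DSMB approval.

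- **Mid-dose sentinels to Cohort 1, and high-dose sentinels to Cohort 2.** Sentinels must "undergo a 7-day observation period for safety and reactogenicity before additional participants are enrolled into that dose group" (4.1). The sequence text then makes completion of those 7 days an explicit condition at both gates.
- **Mid-dose group to high-dose sentinels.** The step above 100 ug opens "Once all 20 participants have received their mid-dose vaccine without triggering halting rules and is approved to proceed by the DSMB" (4.1, with the same words in the Synopsis and 8.1). The only other ordering statement there is that mid-dose enrollment comes before high-dose enrollment.

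The full-group pause rules are in 12.3. Item 1 is any related grade 4 solicited reaction in the mid- or high-dose groups within 7 days. Item 2 is "Three or more grade 3 (Table 3) solicited local or systemic reaction in the same dose group", at least possibly related, "that lasted at least 48 hours within 7 days after administration of the vaccine". Item 3 uses 24 hours, items 4 to 6 use 28 days and item 7 uses 90 days.

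Solicited reactions are recorded "from the time of the vaccination until 7 days post vaccination (Days 1-7") (11.1). The Appendix 1 schedule has the diary reviewed at two contacts, "Visit 2 Day 3 +/-1 Day" by phone (10.3) and "Visit 3 Day 7 +/-2 Days" in clinic (10.4). Between contacts, 11.2 provides a call line: "Participants will be instructed to call a study team line (attended 24-hours per day) if they experience any grade 4 symptom", and likewise for a severe unsolicited event or an SAE.

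**The concern.** Safety and reactogenicity are the primary objectives, and this gate is the trial's only step above 100 ug. Its condition is that no halting rule has been met. For someone dosed very recently, that can be true only because the window is still open. Item 2 shows this most clearly. It counts grade 3 reactions that have lasted 48 hours, and a person dosed less than 2 days ago cannot yet have one.

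The call line does not close the gap. It is aimed at grade 4 symptoms, severe unsolicited events and SAEs. A solicited grade 3 reaction, such as fatigue that prevents daily activity, need not prompt a call and would normally surface at diary review.

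At stake is whether the DSMB decides on the first 200 ug doses with a complete 7-day reactogenicity record at 100 ug, or with a few of the most recent records still open. The authors wrote a 7-day wait at the other two gates, so its absence here looks like an omission.

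**Working it through.** The plan gives no number for this gate. Its one computed design figure, 15 per group in 14.6, does not bear on it. The check therefore compares windows first and then sizes the gap under stated assumptions.

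**1. Follow-up guaranteed on the 20th mid-dose recipient**

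| | Text as written | With 7 completed days |
|---|---|---|
| Guaranteed days after dosing | 0 | 7 |
| Item 3 (24 hours) complete | not guaranteed | yes |
| Items 1 and 2 (7 days) complete | not guaranteed | yes |
| Items 4 to 6 (28 days) complete | no | no |
| Item 7 (90 days) complete | no | no |

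Dosing is Day 1. The phone contact on Day 3 +/-1 is therefore 1 to 3 days after dosing, and the clinic contact on Day 7 +/-2 is 4 to 8 days after. Neither is guaranteed before the gate.

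**2. How many recipients are affected**

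The documents give no accrual rate. The Synopsis gives up to 12 months in total, 6 months of follow-up and up to 7 months on study.

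- Enrollment period: 12 - 7 = 5 months (21.7 weeks) to 12 - 6 = 6 months (26.1 weeks). Removing 2 weeks for the sentinel holds shortens the lower end to 19.7 weeks.
- Assumed even pace: 60/26.1 = 2.3 to 60/19.7 = 3.0 per week.
- Mid-dose share in Cohort 1 under 2:1 randomization: two thirds, or 1.5 to 2.0 per week.
- Under 7 days from dosing when the 20th is dosed: 1 + (6/7 to 1) x rate = 2.3 to 3.0, so about 2-3 people. The other 17-18 of 20 already have 7 days.
- Under 2 days from dosing: 1 + (1/7 to 2/7) x rate = 1.2 to 1.6, so 1-2 people.

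**3. Effect on item 2**

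Item 2 applies to the 18 full-group mid-dose participants. Assume at most one qualifying reaction per person, independent between people, with a true rate of 2% to 10%. The documents give no such rate. Let k be the number of late recipients not counted at the gate. The chance that the rule is met only after they are counted is P(at least 3 of 18) - P(at least 3 of 18 - k).

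| Rate | P(>=3 of 18) | P(>=3 of 17) | P(>=3 of 16) | P(>=3 of 15) | k=1 | k=2 | k=3 |
|---|---|---|---|---|---|---|---|
| 2% | 0.0052 | 0.0044 | 0.0037 | 0.0030 | 0.08% | 0.15% | 0.22% |
| 5% | 0.0581 | 0.0503 | 0.0429 | 0.0362 | 0.8% | 1.5% | 2.2% |
| 10% | 0.2662 | 0.2382 | 0.2108 | 0.1841 | 2.8% | 5.5% | 8.2% |

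For a given k these are upper bounds, because they treat none of the last k people as assessable at the gate. In practice some reactions would already have been seen.

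**4. Cost of waiting**

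Seven days is 7/365 = 1.9% of a 12-month study. If the wait runs to the latest permitted clinic visit (Day 9, 8 days after dosing), it is 8/365 = 2.2%.

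**The case against.** The strongest reply is that the design already contains the risk.

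- DSMB approval is mandatory and comes after the 20th dose, so zero days is a floor and not the expected follow-up.
- The 12.3 pause does not stop at this gate. If a late 100 ug recipient completes the item 2 count after the sentinels open, enrollment stops until the DSMB has reviewed it.
- Only two people can receive 200 ug early. Their own 7-day hold means every 100 ug recipient has at least 7 days before the other 18 high-dose participants are dosed.
- Each sentinel gate rests on 2 people, whereas this gate would have about 17-18 people with 7 completed days at the assumed pace.
- Section 1.2 reports a phase 1 trial of this vaccine up to 250 ug. Section 2 reports fewer systemic reactions in lung recipients than in healthy recipients after the 100 ug third dose.

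All of this stands, and it makes the point small. It does not remove it. The text does not say what follow-up the DSMB must have seen. The 250 ug experience came with more frequent systemic reactions and is not described as being in lung recipients.

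A reader might infer more than the documents support:

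- *That 12.3 cannot be applied at all to late recipients.* It can: a grade 4 reaction counts as soon as it occurs. Only the 48-hour duration in item 2 is out of reach, and only for those dosed under 2 days earlier. For the others the window is incomplete but not empty.
- *That 0 days against 7 makes this the weakest gate.* The 0 describes one person in the worst case, while the 7 describes everyone at a gate of two.
- *That the plan certainly has no wait.* The DSMB charter and Figure 1 were not available, and either may set one.

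**Conclusion.** The point holds as a low-cost safety improvement with a small gain. In the Synopsis, 4.1 and 8.1, the step to 200 ug can open before the 7-day criteria are complete in the last few 100 ug recipients, whereas both neighbouring gates require 7 completed days.

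About 2-3 of 20 people are affected on an assumed even pace. The chance that item 2 is reached only once the last 1-3 are counted is at most about 0.1-0.2% at an assumed 2% rate, 0.8-2.2% at 5% and 2.8-8.2% at 10%. These rates and the pace are assumptions, because the documents supply neither. It would also be wrong to read these percentages as a probability of harm. They describe a pause for DSMB review that would come after up to two people had received 200 ug instead of before.

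The text should be changed because the correction is nearly free, not because the risk is large.

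**What to change.** In the Synopsis, 4.1 and 8.1, and in Figure 1 if it differs, replace the trigger with:

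> Once all 20 mid-dose participants have completed 7 days after vaccination, with the Day 1-7 diary reviewed and no halting rule triggered to date, and the DSMB approves, the high-dose sentinel group (n=2) will be enrolled; all 12.3 criteria continue as rolling pause rules.

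The wording should refer to 7 days completed and not to the Day 7 visit, because that visit may fall on Day 5, only 4 days after dosing. When it does, the remaining diary days can be checked by phone. The 28- and 90-day criteria stay open at this gate, as they do at the sentinel gates, which is why the last clause is needed. If the DSMB charter or Figure 1 already sets this wait, a citation in 4.1 is enough.

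The cost is one delay of about 7-8 days, roughly 2% of the 12-month duration and less where DSMB review overlaps it, plus an occasional phone check. No extra participants, clinic visits, blood draws or assays are needed.

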6.2 Inclusion Criteria

1. All adult lung transplant recipients (age ≥ 18 at the time of consent) who received all of their COVID-19 vaccines after lung transplantation.
2. Received three or four doses of either the Moderna mRNA-1273 or Pfizer BNT162b2 vaccine with the last dose received at least 4 months prior to study enrollment.
3. Currently receiving standard regimen of three drug immunosuppression with prednisone, tacrolimus and mycophenolate mofetil (minimum 250 mg bid) or mycophenolate sodium (minimum 180 mg bid).

4. Agrees not to receive other investigational agents for prophylaxis against COVID-19 including Evusheld monoclonal antibodies for at least 30 days after the study vaccine.
5. Understands and agrees to comply with the study procedures and provides written informed consent.
6. Is in stable health without any new or worsening medical conditions in the opinion of the Investigator.
7. Female participants of childbearing potential (<1 year since start of menopause) may be enrolled in the study if the participant fulfills all the following criteria:
 - a. Has a negative pregnancy test at Visit 1 Day 1.
 - b. Has practiced adequate contraception or has abstained from all activities that could result in pregnancy for at least 28 days prior to the first injection (Day 1).
 - c. Has agreed to continue adequate contraception or practice abstinence through 3 months following the booster injection (Day 90).
 - d. Is not currently breastfeeding.
 - e. Adequate female contraception is defined as consistent and correct use of a Food and Drug Administration (FDA) approved contraceptive method in accordance with the product label. For example:
 - i. Barrier method (such as condoms, diaphragm, or cervical cap) used in conjunction with spermicide
 - ii. Intrauterine device
 - iii. Prescription hormonal contraceptive taken or administered via oral (pill), transdermal (patch), subdermal, or IM route
 - iv. Sterilization of a female participant's monogamous male partner prior to entry into the study
 - v. Note: periodic abstinence (e.g., calendar, ovulation methods) and withdrawal are not acceptable methods of contraception.

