6.3 Exclusion Criteria

1. Previous documented COVID-19 infection.
2. Use of investigational agents for prophylaxis against COVID-19 within 90 days of the start of the study, including Evusheld monoclonal antibodies.
3. Ongoing therapy for acute cellular or antibody mediated rejection.
4. Intravenous immunoglobulins (IVIG) administration within the prior 3 months or ongoing IVIG therapy.
5. Anaphylaxis or allergic reaction to any prior vaccines.
6. History of anaphylaxis or other significant adverse reaction requiring medical intervention after receipt of a vaccine.
7. Is acutely ill or febrile 24 hours prior to or at the Day 1 visit. Fever is defined as a body temperature $\geq 38.0^{\circ}\text{C}/100.4^{\circ}\text{F}$. Participants meeting this criterion may be rescheduled within the

relevant window periods. Afebrile participants with minor illnesses can be enrolled at the discretion of the investigator.

8. Pregnant or breastfeeding.
9. Has a medical, psychiatric, or occupational condition that may pose additional risk as a result of participation, or that could interfere with safety assessments or interpretation of results according to the investigator's judgment.
10. Known history of hypertension (HTN) with systolic blood pressure (BP) > 180 mm Hg at the Day 1 visit.
11. Known history of hypotension with systolic blood pressure < 85 mm Hg at the Day 1 visit.
12. Bleeding disorder considered a contraindication to IM injection or phlebotomy.
13. Active malignancy diagnosed within previous 4 years (excluding non-melanoma skin cancer).
14. Received a major surgery including lung transplantation in the past 3 months.

Exclusion of Specific Populations:

Because the effects on the fetus are not known, pregnant women will not be eligible for the trial. Women of childbearing potential (<1 year since start of menopause) must utilize a highly effective method of contraception and will be required to have a negative urine or serum pregnancy test within 24 hours prior to the vaccination. Children will not be included in this trial as presently there are no children receiving lung transplantation at UCLA. Should the outcome of this trial be deemed acceptable, additional trials may be initiated, including those in other populations.

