10 EVALUATIONS BY VISIT

10.1 Screening/Enrollment Day -30 to 0 (Phone)

1. Pre-screen participants via chart review using HIPAA waiver.
2. Invite eligible participants by phone to participate in study.
3. A qualified member of the study team will review study and provide ICF form. Participants will be asked to sign consent at Visit 1 prior to initiating any study-related procedures.
4. Assign the participant a unique screening number.

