12 DISCONTINUATION AND REPLACEMENT OF PARTICIPANTS

12.1 Screen Failures

Screen failures are defined as participants who consent to participate in the study but are not subsequently assigned to study intervention. A minimal set of screen failure information is required to ensure transparent reporting of screen failure participants to meet the Consolidated Standards of Reporting Trials (CONSORT) publishing requirements and to respond to queries from regulatory authorities. Minimal information includes demography, screen failure details, eligibility criteria, and any SAE.

After the screening assessments have been completed, the PI or qualified designee is to review the inclusion and exclusion criteria and determine the participant's eligibility for the study. Only the following information will be collected on screen failures: demographics (age, screen number, sex, ethnicity, and race, BMI, medication history, co-morbidities including cardiovascular disease, risk factors for cardiovascular disease, and immunosuppressive agents) and reason for ineligibility. Participants who are found to be ineligible will be told the reason for ineligibility.

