12.7 Replacement of Participants

Any participant who is withdrawn or who is lost to follow-up from the study may be replaced at the principal investigator's discretion.

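### Dose is randomised before Visit 1, where consent and final eligibility are settled, and nothing states that enrolling staff are unaware of it until then

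*Combined protocol and SAP*

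**What the plan says.** - **Allocation (synopsis, 4.1, 8.1).** In each cohort of 27, participants are randomised 2:1 (18 to the higher dose, 9 to the standard dose), stratified by number of prior doses and any prior BNT162b2. This is done by the CTSI "statistics team based on scheduled participants prior to the study visit". The six sentinel and initial participants are assigned by visit day and are not part of this point.
- **Consent (10.1).** Screening is by chart and telephone. "Participants will be asked to sign consent at Visit 1 prior to initiating any study-related procedures".
- **Order at Visit 1 (10.2).** Consent is step 1, final eligibility step 7 and the baseline blood draw step 12. Step 13 reads "Confirm group assignment: standard-dose, mid-dose or high-dose group". Step 14 tells the participant the dose and step 15 is the injection. Appendix 1 marks group assignment at Visit 1.
- **Judgement in eligibility (6.2, 6.3).** One inclusion criterion is "Is in stable health without any new or worsening medical conditions in the opinion of the Investigator". Under the acute-illness exclusion, "Afebrile participants with minor illnesses can be enrolled at the discretion of the investigator". Exclusion 9 also rests on the investigator's judgement.
- **Screen failures (12.1).** "Screen failures are defined as participants who consent to participate in the study but are not subsequently assigned to study intervention". Later in the section, "Only the following information will be collected on screen failures"; the list that follows includes the screen number and the reason for ineligibility, but not an allocated dose.
- **Replacement (12.7).** "Any participant who is withdrawn or who is lost to follow-up from the study may be replaced".
- **Analysis sets (14.1).** The Safety set requires a dose to have been received. The Per-Protocol (PP) set requires compliance and evaluability and is limited to Cohorts 1 and 2. The ITT set takes everyone enrolled into a dose group, dosed or not.

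**The concern.** Randomisation protects a comparison only if the decision to enrol cannot depend on the arm. Here the arm is fixed before the last enrolment decision, that decision includes discretion, and the trial is open-label. If staff knew the dose, a participant with a minor illness or borderline stability could be turned away more readily from 200 ug than from 50 ug in Cohort 2, or from 100 ug than from 50 ug in Cohort 1.

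What is at stake is the set of Day 30 antibody and T-cell comparisons in 14.4. The PP set leaves out the six non-randomised participants, so the plan itself relies on randomisation for these comparisons. The primary safety analysis is descriptive and by dose received; it is not at issue.

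**Working it through.** **1. Order of events, side by side.**

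| Step | Where | When |
|---|---|---|
| Dose randomised from the schedule | Synopsis, 4.1, 8.1 | Before Visit 1 |
| Consent | 10.1; 10.2 step 1 | Visit 1 |
| Final eligibility, partly discretionary | 10.2 step 7; 6.2, 6.3 | Visit 1 |
| Group assignment confirmed | 10.2 step 13; Appendix 1 | Visit 1 |
| Screen failure: consents, then not assigned | 12.1 | Implies assignment after consent |

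Under the first row, someone found ineligible at step 7 already has an allocation, so the definition in 12.1 does not fit. Section 12.7 covers people withdrawn or lost. It does not say what becomes of the allocation of someone found ineligible at Visit 1.

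**2. Who counts such a person.** Not the Safety set (no dose received) and not the PP set. The ITT set might, but it is unclear whether someone rejected at Visit 1 is enrolled, and sections 14.3 to 14.5 give the ITT set no analysis.

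**3. The plan's own figure.** Section 14.6: difference 0.91 − 0.23 = 0.68, SD 0.63, two-sided 0.05, 80% power. The t-test solution is 14.50 per group, rounded up to 15. The stated 15 reproduces.

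**4. Illustrative size.** The documents give no exclusion rate, so these inputs are assumptions: k = 1 to 3 of 18 people allocated to the higher dose are excluded at Visit 1, none at the standard dose, and their mean response differs from the rest by D = 0.25 to 0.5 log10, in either direction. The PP standard arm is 9 + 9 = 18.

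- Shift in the higher-dose mean = (k/18) × D. Low: (1/18) × 0.25 = 0.014. High: (3/18) × 0.5 = 0.083.
- As a share of the planned difference: 0.014/0.68 = 2%; 0.083/0.68 = 12%.
- Standard error = 0.63 × √(1/n₁ + 1/n₂).

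The last column is the rejection rate of the two-sided 5% t-test when there is no true dose effect (noncentral t).

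| Case | SE | Shift/SE | Type I error |
|---|---|---|---|
| 17 v 18, shift 0.014 | 0.213 | 0.065 | 5.05% |
| 15 v 18, shift 0.083 | 0.220 | 0.378 | 6.55% |
| 18 v 18, shift 0.083 (excluded people replaced by others like those kept) | 0.210 | 0.397 | 6.72% |

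Power at a difference of 0.68 is 88.2% at 18 v 18 and 84.9% at 15 v 18, so lost numbers are not the problem.

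**5. What a larger effect would need.** Shifts of 0.1, 0.2 and 0.3 log10 at 18 v 18 would give 7.5%, 15.2% and 28.4%. With 3 of 18 excluded, D would have to be 0.6, 1.2 or 1.8 log10 (shift × 18/3), which is 0.95, 1.9 or 2.9 SD. Nothing in the documents supports differences of that size.

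**The case against.** The strongest reply is that bias needs staff to know the dose before step 7, and the documents do not show that they do. A separate statistics team makes the allocation. The visit sequence first handles assignment at step 13, after consent, eligibility and the baseline draw, and Appendix 1 agrees. A reader might infer from the pre-visit randomisation that enrolling staff see the dose and could select on it; the text does not support that. What remains is narrower. Independent generation does not say when the site learns the result, step 13 speaks of confirming an assignment already made, and step 14 concerns telling participants, not staff.

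A reader might also infer that exclusions by arm could never be detected. That too goes further than the text. Section 12.1 keeps the screen number and the reason for ineligibility, and requires screen-failure details for CONSORT reporting. If CTSI retains its allocation list, linking the two would show exclusions by arm. The plan does not provide for that link, and the listed screen-failure data carry no dose.

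Finally, the endpoints affected are secondary and assay-measured, every bias input is assumed, and no text ties minor illness or unstable health to antibody response. This stands, and it limits the severity.

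**Conclusion.** The point holds as a minor one. The plan sets an order in which dose is randomised before consent and before a partly discretionary eligibility decision. No text supplied keeps that dose from enrolling staff, and the order conflicts with 12.1. Figure 1, and the text between the myopericarditis definition and section 12, could not be checked.

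The size is small: a shift of 0.014 to 0.083 log10 and type I error of at most about 6.7%, resting wholly on the assumed exclusion counts and response differences. It is confined to the secondary Day 30 immunogenicity comparisons. Actual foreknowledge or selective exclusion is not shown. The case for change is that the safeguard is standard and costs little.

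**What to change.** 1. Keep the CTSI stratified 2:1 allocation. Release each dose to the site only after consent, confirmed eligibility and the baseline draw (between steps 12 and 13 of 10.2), and state that enrolling staff are unaware of it until then.
2. At release, take the next unused allocation in the participant's stratum instead of allocating to named scheduled participants. An exclusion before release then uses up no allocation and is a screen failure exactly as 12.1 defines it. Handing a named person's unused allocation to the next scheduled person could fail, because that person may already hold one.
3. Report by allocated arm, with reasons, anyone released to a dose but not dosed.
4. Reconcile the synopsis, 4.1, 8.1, 10.2, 12.1 and Appendix 1 on the order of consent, eligibility and assignment. If release is already late in practice, most of this is writing it down.

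**Cost.** Protocol wording, same-day release and a short dispensing wait at up to 27 + 27 = 54 visits; no extra visits or blood draws. CTSI must also decide how firmly to hold 18:9 over the 2 × 2 = 4 strata. With plain blocks of 3 in each stratum, a cohort of 27 could end anywhere from 16:11 to 20:7, with about a 51% chance of exactly 18:9 (simulated under assumed stratum mixes). If the total is fixed at 18:9, the last few assignments can still be guessed, and late release does not cure that.
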